2.3.2 KNOWN POTENTIAL BENEFITS

Three Phase 2 studies have demonstrated that gemcabene is efficacious in reducing LDL-C in hypercholesterolemic patients. As many NAFLD patients have high LDL-C, this is a potential benefit for the participants.

Gemcabene has also been demonstrated to reduce TG, LDL-C, ApoB and hsCRP, all associated with cardiovascular disease risk. This is also a potential benefit to the participants.

Within the study, participants will benefit from receive lifestyle counseling, the current standard of care for pediatric NAFLD. They will also receive regular assessments of their liver disease including labs (ALT, AST and GGT) and hepatic steatosis (MRI).

Long range benefits could include satisfaction from contributing to development of treatments for NAFLD.

2.3.3 ASSESSMENT OF POTENTIAL RISKS AND BENEFITS

The rationale for the necessity of exposing participants to the risks of participating in this study is that medications for NAFLD in children are needed. Risks to children in this study are being minimized by using a low dose of the medication that has proven to be safe over twelve weeks in studies in adults. Further, risk is being minimized by using non-invasive measurement of the liver (MRI) as well as using pediatric experienced staff for the blood draws.

The value of the information to be gained outweighs the risks because the risks are minimal based on the data from the studies in adults and the potential value to improve NAFLD in children is high. Children in the study will benefit from receiving standard of care lifestyle counseling and from state of the art measurements of their liver disease.

3 ENDPOINTS

Primary Endpoint:

- Percent change in ALT from Baseline to Week 12

Secondary Endpoints:

- Absolute change in ALT from Baseline to Weeks 6 and 12
- Percent change in ALT from Baseline to Week 6 and the mean of Week 6 and Week 12
- Absolute change and percent change in hepatic steatosis from Baseline to Week 12 as measured by MRI (volumetric fat fraction-hepafat)
- Absolute change and percent change in pancreatic fat from Baseline to Week 12 as measured by MRI (HepaFat)
- Absolute change and percent change in AST from Baseline to Week 6 and Week 12
- Absolute change and percent change in insulin sensitivity as assessed by fasting insulin, fasting glucose, and HOMA-IR from Baseline to Week 6 and Week 12
- Absolute change and percent change in GGT from Baseline to Week 6 and Week 12
- Absolute change and percent change in serum lipids including total cholesterol, non-HDL-C, HDL-C, VLDL-C, LDL-C, and triglycerides (TG) from Baseline to Week 6 and Week 12
- Absolute change and percent change in apolipoproteins including apoA-1, apoB, apoC-II, apoE and apoCIII
- Absolute change and percent change in inflammatory markers such as hsCRP, IL-1B, IL-6 and procollagen III.
- Absolute change and percent change in lipoprotein particle sizes (VLDL, HDL, LDL, chylomicrons [NMR])
- Absolute change and percent change in post-prandial lipids (total cholesterol, non-HDL-C, HDL-C, VLDL-C, LDL-C, TG, lipoprotein particle size)
- Absolute change and percent change in rate of de novo lipogenesis using stable isotope tracers
- Change in body composition measures by AMRA from Baseline to Week 12
- Absolute change and percent change in liver inflammation and fibrosis (LIF and cT1) scores by MRI (Liver MultiScan).
- Absolute change and percent change in anthropometric measures including height, weight, body mass index, and waist circumference from Baseline to Week 12

- Safety related endpoints including adverse events (AEs), vital signs, clinical labs, hematology and urinalysis
 - Treatment tolerance and compliance
-

4 STUDY DESIGN

4.1 OVERALL DESIGN

Hypothesis

Gemcabene (300mg a day) for twelve weeks will be safe and will decrease ALT and percent hepatic steatosis by MRI in children with NAFLD.

Type of trial

- Phase 2a open label trial
- Multicenter, prospective, open label trial in 40 children (36 who complete the study) with NAFLD

Treatment group

- Gemcabene 300 mg once a day

Number of clinical centers

- 3 pediatric sites

4.2 SCIENTIFIC RATIONALE FOR STUDY DESIGN

The scientific rationale for this phase 2a, open label trial in children with NAFLD is based on critical factors emanating from both the disease and the investigational product. NAFLD trials are challenging because of the large placebo response rate, estimated to be from 20-40%. The placebo response is likely in part due to response to lifestyle changes (improved diet and increased exercise) which is co administered in most trials. A placebo-controlled trial would require a much larger sample size (~140 subjects) in order to test response of ALT in gemcabene compared to placebo. Because this is the first study in children, a smaller study design was selected – an open label single arm study. The problem of placebo response is managed in two ways. First, the sample size was made large enough to allow detection of a greater than historical placebo response rate. Second, there will be a 4-6 week dietary lead in period between screening and initiation of gemcabene (baseline). This will moderate the effects of the dietary and exercise changes in response to counseling.

Children ages 12 years and older were selected for this study because there is not yet juvenile toxicity data to support testing in younger children.

Children diagnosed with NAFLD by either liver biopsy or by MRI will be included because routine clinical practice is quickly moving away from the use of liver biopsies with the advent of easily accessible and accurate MRI based hepatic fat measurement. To ensure that very mild cases of NAFLD are not

included, children must have an elevated ALT 2 x ULN (≥ 54 U/L for boys and ≥ 46 U/L for girls) at the time of screening (demonstrating increased likelihood of ongoing inflammation in the liver). To assess inflammation change in historical ALT (within three months prior to screening) will be obtained (if available). If the ALT at screening is more than two times the historic value, or there is no historic value available, the subject will be asked to repeat the screening ALT after four weeks. If the repeat ALT is greater than 50% increased or decreased over the screening ALT a third ALT will be obtained. If a third ALT is not within 50% of the previous value the subject may be re-screened at a later date.

ALT and hepatic steatosis have been selected as the two non-invasive biomarkers of response of NAFLD to gemcabene because they are non-invasive and are generally accepted as representing improvement in liver histology, which has been linked to clinical outcomes^{35,36}. Importantly, both ALT and hepatic steatosis are related to NAFLD biology and are sensitive to change.

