5.3 LIFESTYLE CONSIDERATIONS

All participants will be required to have attempted lifestyle changes as a treatment for their NAFLD. This will include attempting a dietary improvement and physical activity. Because of the highly variable success with this, no specific requirement for weight loss will be set.

Within the trial, all children will be given standardized lifestyle-based treatment at the Baseline visit. These will consist of the American Heart Association recommended healthy eating pattern for children (http://www.heart.org/HEARTORG/HealthyLiving/Dietary-Recommendations-for-Healthy-Children_UCM_303886_Article.jsp#.WZx7NOMQwaY).

It is important that participants are instructed to not undertake any form of strenuous physical activity for at least 24 hours prior to blood testing.

All clinic visit assessments except screening require the children to fast overnight. This is defined as no food or caloric beverages for a minimum of eight hours prior to sample collection. They will be permitted to have water and it will be encouraged in the evening and in the morning before the visit to promote good hydration.

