9 STATISTICAL CONSIDERATIONS

9.1 STATISTICAL HYPOTHESES

The primary end-point of the study and on which the statistical power is based is the percent change in ALT from Baseline to Week 12.

The hypothesis being tested is that treatment with gemcabene for twelve weeks will result in a clinically meaningful reduction in ALT, in pediatric NAFLD participants.

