9.2 SAMPLE SIZE DETERMINATION

The sample size for this study is 36 completed participants. A percent change from baseline of approximately 20% is considered to be clinically meaningful. Assuming a two-sided test at the 5% significance level, 36 completed participants will provide 81% power to detect a percent change from baseline of 20% (effect size = 0.5), if the standard deviation is 40%. Additionally, assuming a drop-out rate of 10%, a total of 40 participants is needed for enrollment into the study to ensure an adequate number of subjects complete the trial. Power was calculated using a two-sided Wilcoxon test with a 0.05 significance level using PASS v. 14.0.8 (Kaysville, UT).

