9.4.2 ANALYSIS OF THE PRIMARY EFFICACY ENDPOINT(S)

For the primary efficacy endpoint, we will use the ITT population. The entire population, regardless of whether or not they took the study medication, will be used in the analysis.

- **Percent change in ALT**
Changes in our primary continuous outcome measures (ALT) from Baseline to the primary endpoint (Week 12), will be examined as percentage change.
$$\left(\left(\frac{\text{postbaseline value} - \text{baseline value}}{\text{baseline value}} \right) \times 100 \right)$$
. Statistically, percent change from Baseline to Week 12 will be tested against the null hypothesis of no change (i.e., percent change = 0) using a one-sample two-sided t-test or a Wilcoxon signed-rank test, in the event that the percent change is non-normally distributed. Output from the t-test will include the mean percent change, its 95% confidence interval and the p-value. If the data are non-normally distributed, the median percent change value and the 25th and 75th percentiles will be presented, along with the p-value from the Wilcoxon signed-rank test.
- Patients with no week 12 measurements will be excluded from the primary efficacy analysis (only observed case data will be used). In a sensitivity analysis, for subjects with missing week 12 data, we will carry forward their week 6 measurements and re-assess the primary outcomes. Similar analyses will be used to examine the mITT and the PPAS datasets.

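### The sample size is said to allow detection of more than the historical placebo response, but the hypothesis, power and primary test use no placebo value

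*Combined protocol and SAP*

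**What the plan says.** Section 4.2 explains the choice of a single open-label arm. It states that "NAFLD trials are challenging because of the large placebo response rate, estimated to be from 20-40" per cent, adds that a placebo-controlled trial would need about 140 subjects, and says placebo response is managed in two ways. The first is that "the sample size was made large enough to allow detection of a greater than historical placebo response rate". The second is a dietary lead-in of 4-6 weeks between screening and Baseline.

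The statistical sections read as follows:

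- **9.1** states the hypothesis that "treatment with gemcabene for twelve weeks will result in a clinically meaningful reduction in ALT". No comparison with placebo is named.
- **9.2** describes a change of about 20% as clinically meaningful and states that "36 completed participants will provide 81% power to detect a percent change from baseline of 20% (effect size = 0.5"), with an SD of 40%, a two-sided 5% level and a Wilcoxon test.
- **9.4.2** states that "percent change from Baseline to Week 12 will be tested against the null hypothesis of no change (i.e., percent change = 0"), by a one-sample t-test, or by a Wilcoxon signed-rank test if the percent change is non-normal.

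On lifestyle, section 5.3 says "Within the trial, all children will be given standardized lifestyle-based treatment at the Baseline visit". Table 1 in section 1.3 also marks counselling at Baseline only, and section 6.1.2 gives the first dose on Study Day 1, the Baseline day in Table 1.

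**The concern.** Section 4.2 makes a factual statement about what the sample size achieves, and offers it as the first answer to the main weakness of a single-arm trial in this disease. If the statement were true, a placebo figure would appear as the null value or as part of the effect size. None does. The 20% in section 9.2 is justified as clinically meaningful, and it equals the bottom of the quoted placebo range, so it does not exceed that range.

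Someone who relies on 4.2 could take a significant primary result to mean that gemcabene did better than historical placebo. The planned test supports only the statement that ALT changed from Baseline. By itself it cannot separate a drug effect from placebo or lifestyle response. Nor does rejecting zero show the clinically meaningful reduction named in 9.1, which 9.2 sets at about 20%. Section 2.2 says the trial is to support later phase 2b and phase 3 work, so what a positive result means matters.

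**Working it through.** **Inputs.** From 9.2: n = 36 completers, SD 40%, change 20%, two-sided alpha 0.05, drop-out 10%. From 9.4.2: null value 0. From 4.2: placebo response 20-40%, scale not defined. Everything labelled an assumption below is not in the plan.

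**1. Reproducing the stated power.** The standardized effect is 20/40 = 0.5 and the noncentrality is 0.5 × √36 = 3.0. With a t critical value of 2.030 (35 df), the two-sided t-test has power 83.1%. For the Wilcoxon test, the effective n is 36 × 3/π = 34.4, giving 81.2%; simulation with 20,000 normal samples gave 81.0%. Enrolment is 36/0.9 = 40. The stated 81% and 40 both reproduce with a null of zero, so no placebo value is contained in the calculation.

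**2. Smallest significant observed fall.** This is 2.030 × SD/√36:

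- SD 30: 10.2%
- SD 40: 13.5%
- SD 60: 20.3%

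At the plan's own SD, a fall below the bottom of the quoted placebo range is enough.

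**3. Reading A: the 20-40% is a mean ALT fall (assumption).** The table gives the chance of a significant test against zero if the whole fall is placebo-type and occurs after Baseline (n = 36, SD 40%).

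| Mean fall | t-test | Wilcoxon |
|---|---|---|
| 5% | 11.3% | 11.0% |
| 10% | 30.9% | 29.6% |
| 20% | 83.1% | 81.2% |
| 30% | 99.2% | 99.0% |
| 40% | >99.9% | >99.9% |

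For a 20% fall at other SDs (t / Wilcoxon): SD 30, 97.3% / 96.7%; SD 50, 64.6% / 62.5%; SD 60, 49.4% / 47.5%. The 5% and 10% rows are assumed values for what might remain after the lead-in and the three months of attempted lifestyle change required in section 5.1.

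**4. Reading B: the 20-40% is a share of responders (assumption).** Suppose responders fall by 30-50% and others do not change. These falls are illustrative and come from no source in the documents. With total SD held at 40%:

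- 20% × 30 = a mean fall of 6%, chance 14%
- 30% × 40 = 12%, chance 40-42%
- 40% × 50 = 20%, chance 81-83%

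If 40% is instead the SD within each group, the last case has total SD √(40² + 0.4 × 0.6 × 50²) = 46.9 and the chance drops to 70% (t-test).

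A test that did address this reading would be an exact binomial with n = 36 at one-sided 2.5%. It would need at least 13/36 responders to exceed 20% (power 74% at a true 40%), or at least 21/36 to exceed 40% (power 65% at a true 60%). The plan has no responder definition and no such test.

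**5. What testing against a placebo value would give.** With a null of -20% (an example) and SD 40%, power is 30-31% for a true fall of 30% and 81-83% for a true fall of 40%. With a null of -40%, a true fall of 60% would be needed for 81-83%.

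**6. A side observation, inferred and not stated in the plan.** The figure of about 140 fits a two-arm trial for a 20-point difference at SD 40% and 80% power: 63 per arm, 126 in total, 126/0.9 = 140. If so, the same 20 points are a difference from placebo there and a change from zero here.

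**The case against.** The strongest reply is that the limit is inherent and disclosed. The synopsis calls the trial proof of concept with preliminary efficacy, section 2.2 leaves proof of efficacy to later trials, and 4.2 says openly that a placebo comparison was judged too large. The test against zero matches the hypotheses in 1.1 and 4.1, which speak only of reducing ALT. Powering for a meaningful difference while testing against zero is ordinary practice. The 20% also has its own basis: section 2.1 reports that week-12 falls below 20% went with failure to improve histology. All of this stands. It limits the consequence but does not make the sentence in 4.2 true.

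A second reply is that the highest chances in the working assume that the range is a mean fall and that all of it recurs after Baseline. This is also right. They are conditional illustrations, not the trial's false-positive rate, and the responder falls are invented for illustration. The residual 5-10% case may be the fairer one; it still gives 11-31%, against a nominal 5%.

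A third reply is that the lead-in deals with placebo response. It is a separate safeguard and cannot supply the property claimed for the sample size. It is also weakened: 4.2 intends it to moderate changes that follow counselling, yet the standardized counselling in the trial is scheduled at the Baseline visit, with the first dose.

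Finally, 9.4.2 already gives a 95% confidence interval on the t-test route, which a reader could set against any historical figure. That is true, but no benchmark is pre-specified, and on the non-normal route no interval is planned.

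**Conclusion.** The concern holds. The plan claims a property that its sample size and primary test do not have, whichever way the 20-40% is read. The power arithmetic itself is correct; what is wrong is the description of it in 4.2.

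At the plan's n and SD, an observed mean fall of 13.5% is significant. The chance of significance with no drug effect depends on how much placebo-type fall follows Baseline: 11-31% for a mean fall of 5-10%, 81-83% for 20% and 99% for 30%. These figures assume normally distributed percent changes, 36 analysed completers, an SD of 40% and, for the 20% and 30% cases, that the quoted range is a mean ALT fall.

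This should be fixed. It narrows what a positive result means and does not make a proof-of-concept trial uninformative.

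**What to change.** **Preferred.**

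- In 4.2, delete the first safeguard or replace it with a statement that the sample size was set for a change from Baseline and uses no historical placebo value.
- In 9.1 and 9.2, state that the 81% power is against no change only.
- In 9.4.2, state that rejecting zero shows a change from Baseline. By itself it does not separate drug effect from placebo or lifestyle response, and does not show a reduction of at least 20%.
- As a supportive analysis, report the 95% confidence interval for percent change beside a pre-specified historical placebo value, with its scale (mean change or responder share) and source.
- Add a confidence interval for the median. At present, "If the data are non-normally distributed, the median percent change value and the 25th and 75th percentiles will be presented" with a p-value, which leaves no interval to set beside the benchmark.

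The cost is wording in four sections and one supportive interval. There are no extra patients and the primary test does not change. The price is a narrower conclusion and a less favourable account of the power.

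**If the sponsor wants to keep the claim in 4.2,** it must define the benchmark, make it the null value and restate the power. This costs more, because it changes the primary hypothesis. Against -20%, for example, 36 completers give 81-83% power only for a true fall of about 40%, and 30-31% for a true fall of 30%. That benchmark also protects only at the lower end of the range: a drug adding nothing would still beat it 30-31% of the time if the placebo fall were 30%, and 81-83% if it were 40%.

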1.2 SCHEMA

1.3 SCHEDULE OF ACTIVITIES (SOA)

Table 1. Schedule of Activities

| | Screening (-6 weeks) | Baseline (Day 1 +/- 2 days) | Week 2 (Day 15+/- 7 days) | Week 6 (Day 43+/- 10 days) | Week 12 (Day 85 +/- 10 days) | Week 16 Follow- up (phone call) Day 113 +/- 10 days | Early Termination Visit | Week 28 Long-Term Follow-up (Month 3) +/- 2 weeks | Week 36 Long-Term Follow-up (Month 6) +/- 2 weeks | Week 60 Long-Term Follow-up (Month 12) +/- 2 weeks |
|--|-------------------------|--------------------------------------|------------------------------------|--|---|---|-------------------------------|---|---|--|
| Informed Consent and HIPAA Authorization | X | | | | | | | | | |
| Review Inclusion/Exclusion Criteria | X | X | | | | | | | | |
| Demographics & Medical History | X | | | | | | | | | |
| Physical Exam | | X | | | X | | X | X | X | X |
| Vital Signs ^A | X | X | X | X | X | | X | X | X | X |
| Standardized lifestyle counseling | | X | | | | | | | | |
| Height, weight, (calculated BMI) waist and hip measurements ^C | X | X | X | X | X | | X | X | X | X |
| Alcohol Use Disorders Identification Test (AUDIT) | X | | | | | | | | | |
| Dietary Assessment (Food Frequency Questionnaire) | | X | | | X | | X | | | |
| MRI | | X | | | X | | X | X | X | X |
| ECG | | X | X | | | | | | | |
| PROMIS Questionnaires (fatigue, depression, anxiety) | | X | | | X | | X | | | |
| Beverage Questionnaire | | X | | | X | | X | | | |
| Tanner Staging (self-administered) | X | | | | | | | | | |
| Physical Activity Assessment (Block) | | X | | | X | | X | | | |
| Local Urine Pregnancy Test (WOCBP) | | X | X | X | X | | X | X | X | X |
| Urinalysis (UA) | X | X | X | X | X | | X | X | X | X |
| Blood Draw ^B | X | X | X | X | X | | X | X | X | X |

| | | | | | | | | | | |
|----------------------------------|---|---|---|---|---|---|---|---|---|---|
| De novo lipogenesis (substudy) | | X | | | X | | | | | |
| Postprandial lipid (substudy) | | X | | | X | | | | | |
| Instructions for Drug Compliance | | X | X | X | | | | | | |
| Drug Dispense | | X | | X | | | | | | |
| Identify clinical follow-up plan | | | | | X | | X | | | |
| Adverse Events Review | | X | X | X | X | X | X | X | X | X |
| Concomitant Medication Review | X | X | X | X | X | X | X | X | X | X |
| Assess Drug Accountability | | | X | X | X | | X | | | |

A – Vital signs to include: temperature, pulse, respirations, and seated blood pressure

B – See details below in Table 2. Blood Draw Schedule

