5 STUDY POPULATION

5.1 INCLUSION CRITERIA

In order to be eligible to participate in this study, an individual must meet all of the following criteria:

1. Provision of signed and dated informed consent form
2. Provision of signed and dated assent, if indicated
3. Stated willingness to comply with all study procedures and availability for the duration of the study
4. Children aged 12-17 years at the time of informed consent
5. History of clinical diagnosis of NAFLD including a, b and c below:
 - a. Medical history eliminating, other chronic liver diseases (for example mitochondrial diseases, hepatotoxic drugs, anorexia nervosa)
 - b. Laboratory studies: negative testing for hepatitis C and normal ceruloplasmin
 - c. Either liver biopsy confirming NAFLD or MRI $> 10\%$ steatosis within the past three years
6. ALT ≥ 54 U/L for boys or ≥ 46 U/L for girls and ≤ 250 U/L at screening visit and within past three months (prior to screening). If ALT at screening is more than two times the historic value (or a historic value is not available), the subject will be asked to repeat the ALT after four weeks. If

the repeat ALT is more than 50% increased or decreased over the screening ALT a third ALT may be obtained. If a third ALT is not within 50% of the previous value then the subject is ineligible, but may be rescreened at a later date.

7. Body weight \geq 60 kg at the time of screening
8. Able to take oral medication and be willing to adhere to the GEM-IIT-601 regimen
9. Minimum of three months of attempted lifestyle modification to treat the NAFLD and agreement to adhere to Lifestyle Considerations (see section 5.3) throughout study duration

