6.1.2 DOSING AND ADMINISTRATION

The dose is 300 mg orally once a day.

The first dose of study drug will be administered at the research site on Study Day 1. On days with a scheduled office visit with blood sample collection, subject will remain fasted and should not take gemcabene until after the blood samples are collected at the site. On all other days, the subject will self-dose: taking study drug at the same time in the morning with a full glass (8 ounces) of water either with or without food. If a subject misses a dose prior to 6:00 PM, then the subject should take their dose. However, if past 6:00 PM, the subject should not dose and then count the dose as a “missed dose.” The subject will resume normal dosing the next day (i.e., do not take two doses the following day).

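### The dietary lead-in in Section 4.2 cannot moderate the response to the trial's counseling, because that counseling is first given at Baseline with the first dose

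*Combined protocol and SAP*

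**What the plan says.** Section 4.2 acknowledges a large placebo response in NAFLD trials, attributes part of it to lifestyle change, and names two ways of managing it. One is the sample size. The other is that "there will be a 4-6 week dietary lead in period between screening and initiation of gemcabene (baseline"), with the stated purpose: "This will moderate the effects of the dietary and exercise changes in response to counseling".

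Section 5.3 places the trial's counseling elsewhere: "all children will be given standardized lifestyle-based treatment at the Baseline visit". Table 1 in Section 1.3 agrees. Its counseling row reads "Standardized lifestyle counseling | | X", with the Screening cell empty, the single mark under Baseline, and nothing later. Baseline is Day 1, and Section 6.1.2 says "The first dose of study drug will be administered at the research site on Study Day 1".

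The primary endpoint is the percent change in ALT from Baseline to Week 12, tested against zero (Section 9.4.2). Section 9.1 words the hypothesis as a result of gemcabene treatment. The entry criteria do include an earlier lifestyle element, criterion 9 of Section 5.1: "Minimum of three months of attempted lifestyle modification to treat the NAFLD and agreement to adhere to Lifestyle Considerations (see section 5.3) throughout study duration".

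**The concern.** A lead-in controls the response to a co-intervention only if the co-intervention starts at the beginning of the lead-in and the baseline value is taken after it. Here the counseling and the drug start together. A child who improves diet or activity because of the Baseline session does so within the 12 weeks credited to gemcabene, and no control arm is available to separate the two.

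The other control named in Section 4.2 does not fill the gap. A larger sample narrows the confidence interval around the total change. It does not remove a lifestyle component from a test against zero. A report relying on Section 4.2 would therefore claim a safeguard against counseling response that the schedule does not provide. The same applies to the other changes measured from Baseline, such as steatosis and lipids.

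**Working it through.** **Plan's own figure.** Section 9.2 gives 36 completers, a 20% change, SD 40%, two-sided 5% level, Wilcoxon test, and 81% power. With the usual efficiency adjustment, the effective n is 36 × 3/π = 34.4, and the noncentral t distribution gives 81.2%. Simulation with normal data (20,000 runs) gives 81.5%. Enrollment is 36/0.9 = 40. The stated figures reproduce and are not in dispute.

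**Timeline.**

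| Interval | Source | Length | Days after standardized counseling |
|---|---|---|---|
| Lead-in, Screening to Baseline | Section 4.2 | 4–6 weeks = 28–42 days | 0 |
| Endpoint, Day 1 to Day 85 | Table 1 | 85 − 1 = 84 days (74–94 with the ±10-day window) | all |

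The ±2-day Baseline window could separate counseling and first dose by a couple of days, which does not alter this.

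**Is there any other dietary content in the lead-in?** The Screening column of Table 1 has none. The diet questionnaire row reads "Dietary Assessment (Food Frequency Questionnaire) | | X | | | X", so it is first completed at Baseline and repeated at Week 12. The beverage questionnaire and the activity assessment follow the same pattern. Section 9 names no analysis of these three instruments.

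**Size.** Let c be the extra percentage-point fall in mean ALT caused by the Baseline counseling. The observed mean change then contains c in full, along with any drug effect and any other non-drug response.

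- Standard error = 40/√36 = 6.67 points.
- Smallest significant observed mean fall = t(0.975, 35 df) × SE = 2.030 × 6.67 = 13.5%.

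The documents do not give c. The values below are assumptions chosen to show a range.

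| Assumed c (points) | c / SE | c / 13.53 |
|---|---|---|
| 1 | 0.15 | 7% |
| 2 | 0.30 | 15% |
| 5 | 0.75 | 37% |

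**Effect on the test.** Suppose gemcabene does nothing and mean ALT falls 5 points for non-drug reasons of any kind. The planned t-test would then be significant 11% of the time instead of 5%; the Wilcoxon test gives about the same. For falls of 10% and 20% the t-test rates are 31% and 83%. Those larger falls represent the whole non-drug response in a single-arm trial and should not be charged to the timing of the counseling.

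**The case against.** The strongest reply is that the practical weight is unproven. The exposure is one session on the AHA eating pattern, with a handout listed in Section 10.1.1.1. It is given to children who have already tried lifestyle change for at least three months and whose disease persisted. Nothing in the documents shows that this moves ALT materially. That stands, and it limits the size of the claim.

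Second, the interval before Baseline is not empty. Children agree at entry to adhere to Section 5.3, enrollment itself may change behavior, and the interval separates the screening ALT from the Baseline ALT. This also stands in part: the lead-in may absorb some effects of joining the trial. It cannot absorb the response to a session that has not yet taken place. One could read the counseling in Section 4.2 as advice given before the trial, but the trial's own session would still be uncovered.

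Third, the lack of a control arm and the test against zero would remain wherever the counseling was placed. That is correct, and this point does not ask for a control arm.

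Fourth, the co-intervention is disclosed in Sections 2.3.2 and 5.3, weight and BMI changes are already analyzed under Section 9.4.3, and Section 9.4.1 promises descriptive statistics for variables of interest. These help. However, the general line in Section 9.4.1 does not name the diet, beverage or activity data, and disclosure elsewhere does not correct the claim in Section 4.2.

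**Conclusion.** The concern holds on the current text. Section 4.2 presents the lead-in as a control on the response to counseling, and the schedule places the only standardized counseling at the end of that lead-in. As scheduled, the primary change estimates gemcabene added to ongoing lifestyle treatment with standardized counseling at Baseline, and it is not attributable to gemcabene alone.

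The timing conclusion needs no assumption. The amount of bias cannot be established from the documents and may be near zero; the 7% to 37% range rests on assumed responses of 1 to 5 points and on the planned n and SD. The case for acting is the inaccurate design claim and the interpretation built on it. It is not a demonstrated large bias.

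**What to change.** **Preferred: keep counseling at Baseline and correct the text.**

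- Section 4.2: remove the lead-in as a control on counseling response, or limit the claim to what the interval does, which is to separate the screening ALT from the Baseline ALT.
- Sections 9.1 and 9.4.2: add a sentence such as *The Baseline-to-Week 12 change estimates gemcabene added to continuing lifestyle treatment, with standardized counseling given at Baseline, and cannot be attributed to gemcabene alone.*
- Tabulate, descriptively, the Baseline-to-Week 12 changes in the diet, beverage and activity data next to the primary result and the planned weight and BMI changes.

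The cost is text edits and one table from data already collected, with no added visits, samples or patients.

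**Alternative: move counseling to Screening,** with at least 4 weeks before the Baseline ALT and MRI. This costs more. It reverses the Version 2.0 change recorded in Section 10.4, so the current timing was deliberate. It may delay some children. About 60 − 40 = 20 children who then fail screening would be counseled. It also puts an intervention inside the stability check of inclusion criterion 6, under which, if the screening ALT is more than twice the historic value or no historic value exists, "the subject will be asked to repeat the ALT after four weeks". It would only moderate the counseling response. Continuing lifestyle change, expectation effects and regression to the mean would remain in the endpoint interval.
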